# **Comparison of Orbital versus Rotational Atherectomy Effects On Coronary Microcirculation in Percutaneous Coronary Intervention**

**Columbia University Medical Center and Cardiovascular Research Foundation**

**Principal Investigator: [name]**

**Scientific basis/Rationale:** The presence of heavily calcified coronary lesions necessitates the use of ablative devices that aid in successful percutaneous coronary intervention (PCI). However, atherectomy devices generate microparticles that embolize to the distal coronary microcirculation and may compromise myocardial tissue perfusion. We hypothesize that the orbital atherectomy system (OAS), a newer generation atherectomy device, reduces the incidence of microcirculatory compromise as compared to older generation rotational atherectomy (RA) due to differences in the mechanism of athero-ablation.

Two mechanisms that deserve particular attention are the eccentric mounting of the OAS crown and the higher flow rates on the vasodilator flush. Firstly, as opposed to rotational atherectomy where the larger, centrally mounted burr may cause obstruction of flow during the atherectomy, the smaller eccentrically mounted crown in OAS allows continuous perfusion during both atherectomy as well as rest periods. Second, both during rest and atherectomy, the flow rates of vasodilatory flush is higher in OAS compared to RA. Combined, these differences in coronary and vasodilator flush flow could lead to improved perfusion of the distal circulation, particularly during the atherectomy runs when risk of embolization is highest.

The loss of microcirculatory function can be transient, with partial or complete restoration of microcirculatory blood flow, or permanent. As shown in studies of patients with acute coronary syndromes, the loss of microcirculatory function is a critical and independent predictor of myocardial recovery and adverse outcomes. The putative protective effects of OAS on coronary microvasculature may therefore be of major clinical significance and impact.

**Central hypothesis:** OAS is associated with lower loss of coronary microcirculatory function as compared to RA.

**Primary Objectives:** To compare the effect of OAS versus RA on coronary microcirculatory function as measured by saline transit time under basal and hyperemic conditions in patients with clinical indication for PCI in whom atherectomy for optimal PCI is clinically warranted.

Fractional flow reserve (FFR), coronary flow reserve (CFR) and the index of microcirculatory resistance (IMR) will be the primary physiological indices recorded

**Exploratory Objectives:** To compare the incidence of peri-PCI myonecrosis with OAS versus RA, as assessed by measurement of CK-MB and Troponin I and in a subgroup of 20 myocardial edema and late gadolinium enhancement on cardiac MRI..

**Rationale:** Lower incidence of microvascular compromise with OAS may be protective against peri-atherectomy microvascular “plugging” and loss of tissue perfusion, and thereby may result in a reduction in peri-PCI myocardial necrosis, potentially protecting left ventricular function. In patients undergoing elective PCI, IMR has been shown to

independently predict PCI-related microvascular damage and peri-procedural myonecrosis.

**Trial Design:** Randomized, prospective, single-center, investigator initiated, study at Columbia University Medical Center (CUMC).

**Sample Size:** 20

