**Inclusion Criteria:**

- 1) Age  $\geq$  18 years
- 2) Patient with an indication for PCI including:
  - i) Angina (stable or unstable),
  - ii) Silent ischemia (a visually estimated target lesion diameter stenosis of  $\geq 70\%$ , a positive non-invasive stress test, or FFR  $\leq 0.80$  must be present),
  - iii) NSTEMI
- 3) Patients will undergo cardiac catheterization and possible or definite PCI with intent to stent using any non-investigational metallic drug-eluting stent (DES)
- 4) Signed written informed consent
- 5) Heavily calcified (severe) lesions necessitating atherectomy.

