**Angiographic Exclusion Criteria:**

- 1) Lesion length  $<20$  mm
- 2) Study target lesion in a bypass graft
- 3) Ostial RCA study target lesion
- 4) Chronic total occlusion (TIMI flow 0/1) study target lesion
- 5) Bifurcation study lesion with a planned dual stent strategy
- 6) In-stent restenosis study target lesion

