#### (5) FFR ( $P_d/P_a$ at hyperemia)

where  $P_a$  is the aortic pressure measured by the guiding catheter at peak hyperemia. PCI is indicated in stenoses with FFR <0.8.

$T_{mn}$  under basal condition followed sequentially by IMR, FFR and CFR under maximum hyperemia will be measured at 3 separate time points: 1) pre-atherectomy, 2) immediately post atherectomy and 3) at the end of the PCI.

	Screening	Procedure	Post Procedure	Discharge
Consent	X			
Medical History	X			
Randomization	X			
CK/MB			X 	
Troponin I			X 	
Physiological Measurements (FFR)		X 		

X 4-8 hours post procedure; if positive again at 12-18 hours

X Physiological measurements (Total coronary flow, Microvascular resistance, Coronary wedge pressure, Coronary flow reserve and Fractional flow reserve) will be taken before and immediately after atherectomy and at the end of PCI)

**Sample Size:** A clinically important difference would be 20% reduction in IMR in OAS, equating to an IMR difference of 7 (SD=8,  $\alpha$  =0.05 and power=0.80) and requiring a total sample size of 20.

**Projected time for completion:** 1 year. CUMC has a large volume for PCI with ~ 3000 number of PCIs per year including ~250 procedures requiring atherectomy.

**Significance of the results:** If OAS is shown to cause lower disruption and loss of coronary microcirculatory function, the use of this atherectomy device may have significant favorable impact on myocardial recovery and function post PCI as compared to RA, potentially leading to prevention of major adverse cardiovascular events.

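### The hypothesis is about loss of microcirculatory function, but the plan does not say whether arms are compared on change or on post-atherectomy IMR, or how the pre-atherectomy reading is used

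*Combined protocol and SAP*

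**What the plan says.** The Central hypothesis reads "OAS is associated with lower loss of coronary microcirculatory function as compared to RA". The Primary Objectives paragraph beside it speaks of the devices' effect on microcirculatory function, without wording about change. FFR, CFR and IMR "will be the primary physiological indices recorded"; none is singled out.

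Under Procedures, item (5), the indices are to be "measured at 3 separate time points: 1) pre-atherectomy, 2) immediately post atherectomy and 3) at the end of the PCI". The schedule table places randomization at screening, so the pre-atherectomy reading comes after allocation. No blinding is described.

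The sample-size paragraph states "A clinically important difference would be 20% reduction in IMR in OAS, equating to an IMR difference of 7 (SD=8", and goes on to "0.05 and power=0.80) and requiring a total sample size of 20". It does not say whether the SD belongs to a single reading or to a change. Table 1 under Preliminary results reports post-atherectomy values only (IMR 21±6 with OAS, 31±7 with RA).

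On lesions, the inclusion list requires "Heavily calcified (severe) lesions necessitating atherectomy" and the angiographic exclusions include "Chronic total occlusion (TIMI flow 0/1) study target lesion". The document gives no definition of loss, no analysis method, no analysis set and no rule for a reading that cannot be obtained.

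**The concern.** In ordinary use, loss means change from an earlier state, and the design collects that earlier state. An analyst following the hypothesis could reasonably subtract the pre-atherectomy IMR from the post-atherectomy IMR. An analyst following the sample-size paragraph or Table 1 could equally compare post-atherectomy values and ignore the earlier reading. Nothing in the plan chooses between these, or selects the baseline-adjusted analysis that uses both readings.

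Two things are at stake. First, a change score carries the noise of both readings. Unless they are very highly correlated it is clearly less precise than adjustment for baseline, and below a correlation of 0.5 it is less precise than ignoring baseline. Second, a change score cannot be computed without a pre-atherectomy reading. A randomized patient whose post-atherectomy IMR was measured would then leave the comparison, although the outcome is in hand. With 20 patients and open allocation, it is better to settle this before any data are seen.

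**Working it through.** **Inputs.** From the sample-size paragraph: difference 7, SD 8, alpha 0.05, power 0.80, 20 in total; 1:1 allocation from Procedures gives 10 per arm. Assumed, because the documents do not say: two-sided test, SD 8 for a single reading at either time point, pre/post correlation r of 0.3, 0.5 or 0.7, and 0, 2 or 4 of 20 baselines missing.

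**The plan's own figure.** n per arm = 2 × (1.960 + 0.842)² × 8² / 7² = 2 × 7.85 × 1.306 = 20.5, so 21 per arm and 42 in total. The stated total of 20 is not reproduced (one-sided: 17 per arm, 34 in total); 20 fits only as a number per arm. This is a separate and larger problem. It matters here because 10 per arm gives 45.7% power by unadjusted t-test (49.9% by normal approximation), so little precision can be spared.

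**Standard deviations.** Change score: 8√(2(1−r)). ANCOVA residual: 8√(1−r²). Their ratio, ANCOVA to change, is √((1+r)/2) = 0.81, 0.87 and 0.92 at r = 0.3, 0.5 and 0.7. SD 8 cancels, so ANCOVA has the smaller SD even if 8 was meant as the SD of a change.

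**Power at 10 per arm, no readings missing.** Bivariate normal simulation with 40,000 replicates; the change-score and unadjusted columns agree with the exact t-test.

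| r | Change SD | ANCOVA residual SD | Change score | ANCOVA | Unadjusted post value |
|---|---|---|---|---|---|
| 0.3 | 9.47 | 7.63 | 35% | 47% | 46% |
| 0.5 | 8.00 | 6.93 | 46% | 54% | 46% |
| 0.7 | 6.20 | 5.71 | 67% | 71% | 46% |

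Smaller runs put the ANCOVA figure at r = 0.3 between 46% and 48%. Putting the residual SDs into the normal-approximation formula would give ANCOVA 54%, 62% and 78%, which is too optimistic at this sample size.

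**Power with 4 of 20 baselines missing at random.**

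| r | Change, complete cases | ANCOVA, complete cases | ANCOVA, all 20, pooled-mean baseline | Unadjusted post value, all 20 |
|---|---|---|---|---|
| 0.3 | 28% | 37% | 47% | 46% |
| 0.5 | 37% | 43% | 52% | 46% |
| 0.7 | 56% | 59% | 63% | 46% |

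With 2 missing at r = 0.5 the four figures are 41%, 49%, 53% and 46%. Type I error of the pooled-mean analysis is about 5% when readings are missing at random.

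**Stress test of the pooled-mean rule.** Assume no true difference, and that the 4 highest baselines are missing in one arm only. This is an extreme case, chosen to show the direction.

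| r | Pooled-mean ANCOVA: bias, type I error | Complete-case change: bias, type I error |
|---|---|---|
| 0.5 | 2.0 units, about 8% | 2.4 units, about 9% |
| 0.7 | 2.8 units, about 12% | 1.4 units, about 7% |

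The unadjusted post-value comparison and complete-case ANCOVA stay at about zero bias and 5% in both rows.

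**The case against.** The strongest reply is that the plan never commits to a change score. The Primary Objectives paragraph has no change wording. The sample-size paragraph describes a between-arm IMR difference; 7 as a 20% reduction implies a reference level of 7 / 0.20 = 35, which is a level and not a change. Table 1 is post-atherectomy only. On that reading nobody is lost. This stands, and it makes the cost conditional on how loss is analysed. It does not remove the gap, because the plan does not choose that reading either, and a plain post-value comparison leaves the collected baseline unused.

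A reader might infer that tight calcified lesions will prevent the pre-atherectomy reading and that those patients will therefore drop out. The documents do not support this. They nowhere say that an eligible lesion can block the wire or spoil the thermodilution curve, and they give no failure rate. The text introducing item (5) bases the PCI indication on FFR, which presupposes a wire across the lesion. That is not conclusive the other way: the inclusion criteria mention FFR only under silent ischemia, as one of three alternatives, and FFR needs pressures whereas IMR also needs a readable transit time. Failed readings are therefore possible but of unknown frequency.

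A reader might also infer that a complete-case loss score would be biased by a calculable amount. It could be biased if effort to obtain the reading differed by known allocation, but nothing in the documents shows who would be missing, so no size can be given.

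Finally, the pooled-mean rule is not free of assumptions, as the stress test shows, and at r = 0.3 ANCOVA gains almost nothing over the unadjusted comparison. Both points stand and shape the fix.

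**Conclusion.** The firm finding is an unspecified endpoint and analysis: loss is hypothesised, three readings are scheduled, and the plan does not say how the first enters the comparison. If loss is analysed as change, power at 10 per arm is about 46% against 54% with baseline adjustment at r = 0.5, and about 35% against 47% at r = 0.3; at r = 0.7 the gap narrows to about 4 points. Each missing baseline adds to the cost under a change score: with 4 of 20 absent at random and r = 0.5, 37% against 52% when all patients are kept.

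These sizes rest on SD 8 applying to each reading, a two-sided test, normality, and correlations and missing counts that are assumed. That ANCOVA has a smaller SD than change does not depend on how SD 8 is read. The issue is secondary to the sample-size shortfall, but much cheaper to correct.

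**What to change.** State in the analysis section, before any outcome data are seen:

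- The outcome is IMR immediately after atherectomy. Arms are compared by ANCOVA with treatment and pre-atherectomy IMR as covariates. Under randomization the treatment coefficient is the arm difference at equal starting IMR, which addresses the loss hypothesis.
- Every randomized patient with a post-atherectomy IMR is included, whether or not the earlier reading was obtained.
- If a few pre-atherectomy values are missing, each is set to the mean of the observed values pooled over both arms, without using arm or outcome.
- The number of missing pre-atherectomy readings and the reasons are reported by arm.
- The unadjusted comparison of post-atherectomy IMR in all these patients is given as a sensitivity analysis, because the pooled-mean rule is biased if missingness depends on both arm and baseline IMR.

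The cost is one degree of freedom, a few sentences and one recorded reason code. It needs no added patients, procedures or measurements. Adjustment is partly lost for patients whose baseline is filled in, and if the true correlation is low the gain over the unadjusted comparison is negligible.

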### Procedures:

**Physiological indices:** Subjects will be randomized on a 1:1 basis to OAS versus RA. In both groups, we will perform sequential physiological interrogation of the coronary vasculature before and immediately after atherectomy and at the end of PCI, utilizing a direct and robust assessment of microvascular function. This will be achieved by measurement of the mean transit time ( $T_{mn}$ ) of saline using a single pressure-temperature sensor-tipped coronary wire (Certus™ guidewire, St Jude Medical, St Paul, Minnesota). The following parameters will be assessed:

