#### (3) Coronary Wedge Pressure ( $P_w$ )

In addition to the IMR we will assess the coronary wedge pressure, measured by trapping the pressure transducer on the pressure wire with a proximally inflated balloon. Measurements will be taken immediately following atherectomy and then repeated following administration of adenosine and a 3 minute rest period. The difference between the pre and post adenosine coronary wedge pressure will be indicative of the microcirculatory "plugging" caused by atherectomy.

In addition, we will measure  $T_{mn}$  both at rest and at peak hyperemia. If the effects of OAS on the microvasculature are less than RA and the relatively smaller microparticles generated by OAS are more readily "washed out" of the microcirculation with adenosine-induced hyperemia, we expect to see a difference between OAS and RA in  $T_{mn}$  and  $P_d * T_{mn}$  both with resting and hyperemic (i.e. IMR) indices.

We will also use the data to calculate the coronary flow reserve (CFR) that is an index of total blood flow in coronary bed under peak hyperemia relative to rest as described previously.

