#### (4) CFR ( $T_{mn}$ at rest/ $T_{mn}$ at hyperemia)

The indication for PCI will be based on measurement of FFR, the current standard of practice, which will be determined as:

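### IMR is the only index sized but is never named as the sole primary comparison, and neither its post-treatment reading nor the use of its pre-atherectomy value is fixed

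*Combined protocol and SAP*

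**What the plan says.** Five places in the combined protocol and SAP bear on what is primary.

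- **Primary Objectives.** Microcirculatory function is compared "as measured by saline transit time under basal and hyperemic conditions". The next sentence, which carries on the same objective, adds: "Fractional flow reserve (FFR), coronary flow reserve (CFR) and the index of microcirculatory resistance (IMR) will be the primary physiological indices recorded".
- **Central hypothesis.** "OAS is associated with lower loss of coronary microcirculatory function as compared to RA". The word *loss* points to a comparison with the state before atherectomy.
- **Procedures, Physiological indices.** The plan calls for "sequential physiological interrogation of the coronary vasculature before and immediately after atherectomy and at the end of PCI". The section on FFR repeats this: basal transit time "under basal condition followed sequentially by IMR, FFR and CFR under maximum hyperemia will be measured at 3 separate time points".
- **Coronary Wedge Pressure.** The arms are expected to differ in transit time and in pressure times transit time, "both with resting and hyperemic (i.e. IMR) indices".
- **Sample Size** (after the schedule table). One IMR difference of 7, SD 8, alpha 0.05, power 0.80, total 20. No reading, test or model is given, and it is not said whether the SD is that of a single reading or of a change.

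On FFR, the section on CFR says: "The indication for PCI will be based on measurement of FFR, the current standard of practice". The rationale says of the microvascular effect: "The loss of microcirculatory function can be transient, with partial or complete restoration of microcirculatory blood flow, or permanent".

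**The concern.** The plan has one alpha but does not attach it, in words, to one comparison. The objective names transit time, its continuation names three indices, and the sample-size paragraph uses one of them.

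Accepting IMR as primary still leaves two choices open. The first is the reading: straight after atherectomy or at the end of PCI. The protocol's own statement that loss can be transient means the two may give different answers. The second is the model: the post-treatment value alone, the change from before atherectomy, or the post-treatment value adjusted for the earlier one. The baseline is collected and the hypothesis is about loss, yet the baseline has no stated role.

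If these choices are made after results are seen, an IMR p-value below 0.05 cannot be taken at face value. If IMR is null and transit time positive, or the reverse, a reader could not tell whether the primary objective was met.

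**Working it through.** **1. How the named measures relate.** From the plan's formulas, IMR = Pd × Tmn at hyperemia, CFR = Tmn at rest / Tmn at hyperemia, and FFR = Pd/Pa at hyperemia. IMR and CFR are therefore built from transit time, and for these two the objective and its continuation describe one family of measurements. FFR contains no transit time. It reflects the epicardial stenosis, which the procedure itself changes, and the plan uses it as the indication for PCI.

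**2. The plan's own figure.** Inputs from Sample Size: difference 7, SD 8, alpha 0.05, power 0.80; 1:1 allocation from Procedures. Sidedness is not stated, so two-sided is assumed. Per arm, n = 2 × [(1.960 + 0.842) × 8/7]² = 20.5, so 21 per arm and 42 in total (44 by t-test), against the stated total of 20. With 10 per arm the standard error is 8 × √(2/10) = 3.58, the noncentrality is 7/3.58 = 1.96, and power on 18 df is 46%. This shortfall is a separate matter; 46% serves here only as the unadjusted reference.

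**3. False-positive chance if choices are open.** IMR only, no true difference, normal data, 10 per arm, each test two-sided at 5% (t-tests on 18 df, ANCOVA on 17 df), with any significant result counted. The documents give no correlations, so a range is assumed.

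- *Reading open, unadjusted tests.* 9.7%, 9.1%, 8.4% and 7.1% at between-reading correlation 0, 0.5, 0.7 and 0.9. Check at 0: 1 − 0.95² = 9.75%.
- *Model open at one reading* (post value, change or ANCOVA). 8.8% to 10.4% over correlations 0 to 0.9.
- *Both open* (two readings × three models). 15.0% to 17.6%.

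**4. Power for a difference of 7 under each model.** SD 8 is taken as that of one reading, and ρ is the assumed correlation of pre-atherectomy IMR with the tested reading. The ANCOVA SD is 8√(1 − ρ²), with variance multiplied by 1 + 1/16 for estimating the slope, on 17 df. The change-score SD is 8√(2(1 − ρ)), on 18 df. Example at ρ = 0.7: the ANCOVA SE is 8 × √0.51 × √(0.2 × 1.0625) = 2.63; the change-score SE is 8 × √0.6 × √0.2 = 2.77.

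| ρ | Post value only | ANCOVA | Change score |
|---|---|---|---|
| 0 | 46% | 43% | 26% |
| 0.5 | 46% | 54% | 46% |
| 0.7 | 46% | 71% | 67% |
| 0.8 | 46% | 85% | 83% |

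ANCOVA passes the unadjusted test above ρ of about 0.26. It leads the change score up to at least 0.85 and is within 0.2 points of it at 0.9.

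**The case against.** The strongest reply is that IMR is plainly the endpoint. It alone has a difference, an alpha and a power. Transit time is the measuring technique and the indices are its outputs, so the objective and its continuation are one statement. The list speaks of indices *recorded*, which may be only a list of measurements. The reading can also be guessed: the pilot IMRs in Table 1 were taken post-atherectomy, and the rationale places the greatest embolization risk at the atherectomy runs.

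Much of this stands. A reader might infer that the plan sets up three rival primary sets of two, three and one measures. The overlap shown above does not support that. A reader might also infer an error rate near 26%, from three indices at two readings. That needs six independent tests, which the formulas rule out: IMR and CFR share hyperemic transit time, IMR and FFR share distal pressure, and the readings repeat within a patient. The rates above are also two-sided, so a false result in favour of OAS is about half as likely.

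What does not stand is that inference can replace designation. The pilot table is preliminary, nonrandomized data, and no section names a test, a reading or a use for the baseline. Nor can the comparison be excused as exploratory: only the myonecrosis and MRI objectives carry that label.

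It is also fair to say that a prespecified post-value or change-score analysis would close the gap. ANCOVA is preferred on efficiency; it is not the only valid choice.

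**Conclusion.** The point holds as a gap in specification that should be fixed. IMR is the evident main endpoint but is not named as the sole primary. FFR is called primary although it is neither a transit-time nor a microvascular measure. The tested reading and the role of the pre-atherectomy IMR are unstated.

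If choices were free, the nominal 5% becomes about 7-10% with the reading open, 9-10% with the model open and 15-18% with both. These figures are conditional on assumed correlations and on any favourable result being counted. The plan does not say that any one result suffices, so they measure exposure and are not the trial's actual error rate. The power comparison assumes that SD 8 belongs to a single reading.

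**What to change.** Before any between-arm result is seen:

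1. Name IMR at one stated post-treatment reading, OAS versus RA, as the sole primary comparison at two-sided 0.05. The reading straight after atherectomy matches the pilot table; end of PCI is also defensible. One must be chosen.
2. Analyse it by ANCOVA with arm and pre-atherectomy IMR, and report the adjusted difference with its 95% CI.
3. Reword the primary objective, which now names transit time, to IMR at that reading, and remove *primary* from the list of indices.
4. Make the other IMR reading, CFR, resting and hyperemic transit time and wedge pressure secondary, with no confirmatory claim. Report FFR descriptively.

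A rule for a missing pre-atherectomy IMR should also be set in advance. Entering the pooled mean of the observed baselines is one option, not a requirement. With 2 of 10 baselines missing per arm, it gives 52% power against 44% for dropping those patients at ρ = 0.5, but 72% against 74% at ρ = 0.8.

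The cost is protocol wording, one degree of freedom (46% to 43% power if the baseline is uncorrelated with the later reading), and no primary claim on the other measures. No patient, visit or measurement is added. None of this repairs the separate shortfall of 20 patients against the stated 80% power.

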#### (2) Microvascular resistance ( $P_d * T_{mn}$ )

Extrapolating from Ohm's law, distal coronary pressure ( $P_d$ ) divided by the inverse of the hyperemic mean transit time (a correlate to absolute flow), measured simultaneously with the coronary pressure wire, will evaluate microvascular resistance. Under peak hyperemia (achieved by intravenous infusion of adenosine at 140  $\mu$ g/kg/min) this ratio has been called the IMR^3. IMR is derived from the assumption that at peak hyperemia the variability of resting vascular tone and hemodynamics will be eliminated, and the *minimum* microvascular resistance will be achieved.

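### FFR is listed as a primary index for a microcirculatory objective, although it contains no transit time and can be higher when the microcirculation is worse

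*Combined protocol and SAP*

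**What the plan says.** The Central hypothesis is that "OAS is associated with lower loss of coronary microcirculatory function as compared to RA". The Primary Objectives paragraph begins "To compare the effect of OAS versus RA on coronary microcirculatory function as measured by saline transit time under basal and hyperemic conditions". The sentence that completes it reads "Fractional flow reserve (FFR), coronary flow reserve (CFR) and the index of microcirculatory resistance (IMR) will be the primary physiological indices recorded". It gives no order among the three indices and no rule for reading any of them.

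The Procedures section defines each index:
- Item (2): IMR is distal pressure times hyperemic transit time. The reasoning is Ohm's law, with distal pressure "divided by the inverse of the hyperemic mean transit time (a correlate to absolute flow").
- Item (4): CFR is resting transit time over hyperemic transit time.
- Item (5): FFR is distal pressure over aortic pressure at hyperemia, where aortic pressure "is the aortic pressure measured by the guiding catheter at peak hyperemia".

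FFR also has a separate job: "The indication for PCI will be based on measurement of FFR". It is measured at three time points: before atherectomy, immediately after it, and at the end of PCI.

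**The concern.** CFR and IMR are both built from transit time, which is how the objective says microcirculatory function is measured. FFR is not. It is a ratio of two pressures, and it depends on how much epicardial narrowing remains as well as on the resistance of the bed beyond it.

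The direction is also a problem. A higher IMR means a worse microcirculation, while a higher FFR is ordinarily read as a better result. If microvascular plugging raises both, the two primary indices would appear to disagree about which device did less harm. A device that simply opened the lumen more would also show a higher FFR, whatever it did downstream. Because the plan gives no ranking and no reading rule, either pattern could be reported as a primary result on the central hypothesis, which FFR cannot test.

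**Working it through.** **The plan's own figures.** The plan gives no expected FFR value or FFR difference, so there is none to reproduce. The contrast used here comes from the Sample Size paragraph, where a 20% reduction equals an IMR difference of 7. The comparator is then 7 / 0.20 = 35 and the OAS arm 35 − 7 = 28. (The stated total of 20 does not follow from a difference of 7, SD 8, alpha 0.05 and power 0.80: the normal approximation gives 21 per arm two-sided, 42 in total. That is a separate matter and does not affect this point.)

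**Inputs.**
- Microvascular resistance Rm: IMR 28 versus 35 (Sample Size), or 21 versus 31 (Preliminary results, Table 1; nonrandomized, 6 and 4 patients).
- Residual epicardial resistance Re: not in the documents. Assumed 3 to 10 in the same units as IMR, and equal in both arms.
- Venous pressure and collateral flow are neglected.

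**Formula.** Extend the Ohm's-law reasoning of Procedures item (2) to two resistances in series with flow Q. Then Pd = Q × Rm and Pa − Pd = Q × Re, so

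FFR = Pd/Pa = Rm / (Rm + Re).

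The derivative with respect to Rm is Re / (Rm + Re)², which is positive whenever Re > 0.

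**Results with equal Re in both arms.**

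| Re | Rm 28 | Rm 35 | Gap | Rm 21 | Rm 31 | Gap |
|---|---|---|---|---|---|---|
| 3 | 28/31 = 0.903 | 35/38 = 0.921 | 0.018 | 21/24 = 0.875 | 31/34 = 0.912 | 0.037 |
| 5 | 28/33 = 0.848 | 35/40 = 0.875 | 0.027 | 21/26 = 0.808 | 31/36 = 0.861 | 0.053 |
| 8 | 28/36 = 0.778 | 35/43 = 0.814 | 0.036 | 21/29 = 0.724 | 31/39 = 0.795 | 0.071 |
| 10 | 28/38 = 0.737 | 35/45 = 0.778 | 0.041 | 21/31 = 0.677 | 31/41 = 0.756 | 0.079 |

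In every row the arm with the higher microvascular resistance has the higher FFR.

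**Little residual stenosis.** Fix FFR in the low-resistance arm (Rm = 28), solve Re = 28 × (1/FFR − 1), and apply the same Re to Rm = 35:
- FFR 0.90: Re = 3.11, other arm 0.918, gap 0.018.
- FFR 0.95: Re = 1.47, other arm 0.960, gap 0.010.
- FFR 0.98: Re = 0.57, other arm 0.984, gap 0.004.

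**Venous pressure.** With an assumed aortic pressure of 90 mmHg and venous pressure of 5 or 10 mmHg, FFR 0.80 in the low-resistance arm becomes 0.833 or 0.832 in the other arm, and 0.90 becomes 0.918 in both cases. The results change by 0.001 or less.

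**Unequal residual stenosis.** FFR depends only on the ratio Re/Rm. At 28 versus 35 the two arms have equal FFR when Re in the low-resistance arm is 28/35 = 0.80 of that in the other arm. Below that ratio the low-resistance arm has the higher FFR; above it, the lower. The documents give no information on residual stenosis by device, so the sign cannot be predicted.

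**The case against.** The strongest reply is that the plan never uses FFR to test the hypothesis. The sentence calls the three indices recorded, not endpoints. The objective's wording rests on transit time, which leaves FFR out. Procedures item (3) predicts a device difference in transit time and in pressure times transit time, without naming FFR. The sample size rests on IMR alone. Table 1 reports flow, IMR and wedge pressure, with no FFR. All of this is correct, and it limits the practical consequence. It does not remove the word primary from FFR, and no section says how an FFR difference between arms should be read.

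The second reply concerns size, and it also stands. The pilot contrast roughly doubles the gap obtained from the plan's own planning difference, the values of Re have no anchor in the documents, and the sign depends on Re being equal across two different ablation devices.

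A reader might infer more: that FFR is a formal primary endpoint, that it will rank the devices the wrong way round, or that the gap matters because it lies near 0.80. The documents support none of these. No endpoint or FFR comparison is named. The reversal is one scenario that fades as FFR approaches 1. The 0.80 value serves in the plan as a threshold for PCI, not as an outcome after atherectomy, so it carries no weight here whichever side of it a modelled value falls.

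**Conclusion.** The point holds as a minor one. FFR is the wrong kind of index for the stated objective: by the plan's own definitions it contains no transit time and combines epicardial and microvascular resistance. The directional result rests on a two-resistance series model, IMR standing in for microvascular resistance, and equal non-zero residual epicardial resistance in both arms. Under those assumptions the possible distortion is a few hundredths of FFR where stenosis remains, as it may immediately after atherectomy. It is negligible once the lesion is well opened, where FFR simply says little about the microcirculation. Without equal residual resistance, the safe conclusion is that an FFR difference cannot be attributed to the microcirculation in either direction.

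**What to change.** In Primary Objectives, remove FFR from the list of primary indices and name IMR, the only index with a sample-size basis, as the primary index. Keep every FFR reading as a descriptor of the lesion and of residual stenosis, and leave its role in the PCI indication as written. Add one sentence stating that a between-arm difference in FFR is not evidence for or against the central hypothesis.

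The cost is an edit of a sentence or two, with no change to measurements, procedures or sample size. FFR can no longer be cited as a primary index. Naming IMR alone also moves CFR to a supporting role, although nothing above counts against CFR, which is built from transit time.
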